### **Study Protocol**

A screening visit occurred in Human Nutrition Lab (HNL) from late September to early November during which a Likert item was administered to measure self-weighing frequency habits. Existing (or history of) eating disorders was determined by Drive for Objective Thinness Questionnaire which resulted in study exclusion. Qualified subjects were randomized into either the DSW+GF or control group (balanced blocks by age, sex, and BMI) by research personnel.

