### **Statistical Analysis**

Statistical analyses were performed using JMP Pro 13 (Statistical Discovery™, From SAS Institute Inc., Cary, NC). A sensitivity power analysis to determine the smallest detectable effect size (was performed using G\*Power, 3.1.9.2). Assuming scores at pre-holiday were

correlated with post-holiday with at least a correlation of  $r = .40$ , our study was poised to detect differences in change scores from time 1 to time 2 of Cohen's  $f = .15$  (small-to-medium) effects. To test the treatment effects on BW across visits, as well as on the change between visits, a full factorial repeated measures ANOVA (mixed-methods) was conducted based on sex and initial BMI (normal weight (NW), and overweight and obese (OW&OB)). Participants with the BMI of 18.5-24.9kg/m^2 were categorized as NW and those with a BMI $\geq 25$ kg/m^2 were grouped into the OW&OB category. This grouping was done due to the relatively lower number of subjects in the OW or OB categories compared to NW (control group was 69% NW (n=38) and 31% OW&OB (n=17) while the DSW+GF group was 75% NW (n=42) and 25% OW&OB (n=14)). A two-way repeated measures ANOVA was used to test the treatment effects on other anthropometrics (body fat, WC, HC, and waist-to-hip ratio (WHR)), systolic and diastolic blood pressure (SBP and DBP), and blood markers (Total Cholesterol (TC), Triglyceride (TG), High-density Lipoprotein (HDL), Low-density Lipoprotein (LDL), and TC/HDL) across all visits. Post hoc analyses were performed using a Tukey's test. Significance was set at  $p < 0.05$ , and data are presented as mean  $\pm$  SEM unless otherwise specified. Additionally, data collected from questionnaires (except the Likert item), was analyzed using a parallel multiple mediator model to test whether any component of participants' responses was a mediator for the impact of treatments.

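### Allocation was balanced on age, sex and BMI, but the models for the 11 other outcomes name none of them: a possible small precision gain at almost no cost

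*Combined protocol and SAP*

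**What the plan says.** The Study Protocol section describes allocation: "Qualified subjects were randomized into either the DSW+GF or control group (balanced blocks by age, sex, and BMI) by research personnel". It does not say how age and BMI were cut to form the blocks.

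The Statistical Analysis section uses two kinds of model.

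- **Body weight:** "a full factorial repeated measures ANOVA (mixed-methods) was conducted based on sex and initial BMI", with BMI in two categories (normal weight; overweight and obese). Age is not named.
- **The other outcomes:** "A two-way repeated measures ANOVA was used to test the treatment effects on other anthropometrics", and on blood pressure and blood markers, across all visits. The list has 4 + 2 + 5 = 11 outcomes: body fat, waist and hip circumference and their ratio; systolic and diastolic pressure; total cholesterol, triglyceride, HDL, LDL and TC/HDL. No age, sex or BMI term is named. The two factors of these models are not named either; treatment and visit is the natural reading.

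The same section gives a sensitivity power analysis, which says "our study was poised to detect differences in change scores from time 1 to time 2" of Cohen's f = .15, given a pre-post correlation of at least .40. It names no outcome and no power level.

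**The concern.** The investigators judged age, sex and BMI worth balancing, and they used two of the three in the body-weight model. The plan gives no reason for leaving all three out of the other 11 models.

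When a factor is balanced by design and omitted from the model, whatever it explains of the outcome stays in the error term. The standard error is then larger than it needs to be, and the test tends to be slightly conservative. At stake is some precision on 11 outcomes, recoverable from data already collected.

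**Working it through.** **Inputs.** From the Statistical Analysis section: control 38 + 17 = 55, DSW+GF 42 + 14 = 56, so N = 111; f = .15; r = .40; significance at .05. Visits: v1, v2 and v3. Assumed here: R², the share of variance in change that the three factors explain (no value in the documents); complete data; one common correlation between visits and sphericity; and f and r carried over from the plan's change-score statement to these outcomes.

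**1. The plan's own figure.** For a treatment by visit test with two arms and m visits, λ = f²·N·m/(1 − r). With m = 2, λ = 0.0225 × 111 × 2 / 0.6 = 8.325. On F(1, 109) the power is 81.6%. At an assumed 80% power the detectable f is .147, which rounds to the stated .15. The figure reproduces without any covariate.

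**2. The test the 11 models use.** They run across all visits, so m = 3: λ = 0.0225 × 111 × 3 / 0.6 = 12.49 on F(2, 218), giving 89.2% unadjusted.

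**3. What adjustment can remove.** A stable difference between, say, men and women appears at every visit and cancels in treatment by visit. Only the part of a factor that predicts change stays in the error. Main effects alone therefore do nothing for this test; the factor by visit terms matter.

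**4. Adjusted power.** Three covariates with visit interactions take error df from 109 to 106 (two visits) or from 218 to 212 (three visits). With tight balance, λ becomes λ/(1 − R²). If balance is only that of simple randomization, λ is also divided by 1 + 3/105 = 1.029. The excess SE is 1/√(1 − R²) − 1, or 1/√(1.029(1 − R²)) − 1 in the second case.

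| R² of change (assumed) | Three visits: tight / simple | v1–v2 contrast: tight / simple | Unadjusted SE larger by: tight / simple |
|---|---|---|---|
| unadjusted | 89.2% | 81.6% | – |
| 0 | 89.1% / 88.2% | 81.6% / 80.5% | 0% / −1.4% |
| .05 | 90.7% / 89.9% | 83.5% / 82.4% | 2.6% / 1.2% |
| .10 | 92.2% / 91.4% | 85.4% / 84.4% | 5.4% / 3.9% |
| .20 | 94.9% / 94.3% | 89.2% / 88.3% | 11.8% / 10.2% |

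If the error df are left at 218, the three-visit values 91.4% and 94.3% round to 91.5% and 94.4%.

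The tight-balance gains are slightly generous. Under tight balance the unadjusted estimate varies less than its SE says, so the unadjusted test already does better than its nominal power. On a normal approximation for v1–v2, 82.3% becomes 82.9%, 83.5% and 85.0% at R² = .05, .10 and .20.

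**5. Break-even.** Without tight balance, adjustment pays once R² exceeds 1 − 1/1.029 = .028. With tight balance the break-even is essentially zero.

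**6. Direction of error.** Under ideal balance the unadjusted two-sided size is 2(1 − Φ(1.96/√(1 − R²))): 4.4%, 3.9% and 2.8% at R² = .05, .10 and .20. The only realised balance reported is normal weight, 42/56 − 38/55 = .059. Its SD under simple randomization is √(80/111 × 31/111 × (1/55 + 1/56)) = .085, so the gap is 0.69 SD. If the two-level BMI category alone carried the R², the unadjusted estimate would shift by 0.69√R² = 0.16, 0.22 and 0.31 SE, and the size would be 4.7%, 4.4% and 3.8%. Size would pass 5% only with a gap above about 1.0 SD.

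**The case against.** The strongest reply is that an unadjusted ANOVA of randomized arms is legitimate, and that the gain is hypothetical. That largely stands. The omission is a fact of the text; the gain is not. It depends on an R² that the documents do not give, and it can be zero or slightly negative.

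The power baseline is also borrowed. The plan's f and r are tied to no outcome, and r is a lower bound. At r = .60 (an assumption), unadjusted v1–v2 power at f = .15 is already 93.9%, and R² = .05 without tight balance gives only 94.3%. The v1–v2 columns apply only if such a contrast is tested; for the 11 outcomes the plan specifies all visits, so the three-visit figures should lead. The observed BMI gap shows no sign of especially tight balance, so the lower figure in each pair deserves at least equal weight. That is only indicative, because the block cut-points are unknown.

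The section is written in the past tense ("Statistical analyses were performed using JMP Pro 13"). If the analyses are done, adjusted models add a second set of 11 results, which is a cost beyond degrees of freedom.

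Four stronger readings are tempting, and the documents do not support them:

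- **The unadjusted tests are invalid or anti-conservative.** On average they are slightly conservative under balance, and the reported BMI gap is below the point where size would pass 5%. Chance imbalance on a factor that predicts change can still move a single estimate either way.
- **The trial falls short of its stated sensitivity.** The f = .15 figure reproduces without covariates, so adjustment could only add to it.
- **All variation due to age, sex and BMI is lost to error.** Only variation in change is.
- **The body-weight model is deficient for lacking age.** It already carries sex and BMI category. What age would add cannot be sized and may be negligible.

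None of this removes the point for the 11 models, where the likely loss is about one power point at worst.

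**Conclusion.** The point holds as a minor suggestion for the 11 two-way models. Age, sex and BMI were used to balance allocation and are not named in those analyses. Adjusting with visit interactions would raise three-visit power by roughly 1 to 6 points for an R² of change between .05 and .20, and would lose at most about 1 point if the factors predict nothing.

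Confidence is high on the omission and low on the size of the gain. The size rests on the assumed R², on f = .15 and r = .40 applying to these outcomes, on complete data, and on treatment and visit being the two factors.

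**What to change.** In each of the 11 models, name treatment and visit as the two factors. Add sex, continuous age and continuous baseline BMI, each with its visit interaction, and read the treatment effect from treatment by visit. If the unadjusted analyses have already been run, keep them and report the adjusted ones beside them, labelled as added afterwards and not as replacements.

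The cost is no new data, a fall in error df from 109 to 106 between subjects and from 218 to 212 within subjects (complete data), and a second labelled set of results to present.

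For body weight, an age term with its visit interaction is optional. It should be additive: crossing age into the full factorial would split small cells further, since the DSW+GF overweight and obese group has 14 people before division by sex.

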### *Pre-Holiday Visit (v1)*

This visit occurred in HNL within a one-week period prior to Thanksgiving after an 8-12h overnight fast and 12h without exercise. Height, body weight (BW), waist and hip circumference (WC and HC), blood pressure, and body composition using Dual Energy X-Ray Absorptiometry (DXA™; Hologic Inc., Discovery A, Bedford, MA) were measured. A fasting blood draw was taken for blood lipids. Questionnaires administered at this visit included the Perceived Stress Scale (PSS), Three factor Eating Questionnaire (TFEQ), Power of Food Scale, National Insomnia Screening Questionnaire, self-weighing frequency Likert item, Mindful Eating Factors Questionnaire and Fat Preference Questionnaire. To assess participants' perceptions of healthy and unhealthy foods, participants categorized a series of 60 images of different foods accompanied by their names (e.g., pizza, pancake, and broccoli). Participants selected 'healthy' or 'unhealthy' for each food item. This was done to examine whether daily self-weighing with graphical feedback (DSW+GF) would alter subjects' perception of foods, and whether these perceptions, as well as data from our other questionnaires, would be significant mediators for the effects of DSW+GF on BW.

#### *Intervention Period (Holiday Season)*

*Intervention group:* At the conclusion of v1, participants in the DSW+GF group received the Wi-Fi scale (Nokia (Withings®), Paris, France). They were asked to start DSW the day after v1 until their post-holiday visit (v2). They weighed themselves first thing in the morning after voiding (and defecating if that is their normal pattern). Once they stepped on the scale, their data would automatically transfer to their Withings® account and their Withings® mobile app (Nokia Health Mate app). Immediately after a weight measurement, electronic graphical feedback of weight fluctuations appeared on the scale's screen and the app. The average of the first 4 days of BW served as the "baseline" weight, which was then set as the participant's "target" weight in

their Withings® account. This target weight showed up as a straight line on their graph of daily weights. Participants were instructed to try not to gain weight above this target line, and no additional instructions on how to achieve that goal were provided. The GF component of the DSW was the immediate graphical feedback of their weight fluctuations from the scale and how their weight compared to their target “baseline” weight.

*Control group:* Control participants did not receive any intervention; however, they completed the same study visits as the intervention group.

#### *Post-Holiday Visit (v2)*

This visit occurred in HNL within a one-week period after New Year’s Day with the same conditions and procedures as v1. The DSW+GF group was told they could discontinue DSW; however, they were allowed to keep the scales until the follow-up visit and were told to use it as they saw fit.

#### *Follow-up Visit (v3)*

This visit occurred in HNL 14 weeks after v2 under the same conditions and procedures as v1 and v2. The scales were collected from the DSW group and weighing frequency data during the follow-up period was obtained from their Withings® accounts. All participants were debriefed as to the true intent or purpose of the study at the conclusion of this visit.

### **Statistical Analysis**

Statistical analyses were performed using JMP Pro 13 (Statistical Discovery™, From SAS Institute Inc., Cary, NC). A sensitivity power analysis to determine the smallest detectable effect size (was performed using G\*Power, 3.1.9.2). Assuming scores at pre-holiday were

correlated with post-holiday with at least a correlation of  $r = .40$ , our study was poised to detect differences in change scores from time 1 to time 2 of Cohen's  $f = .15$  (small-to-medium) effects. To test the treatment effects on BW across visits, as well as on the change between visits, a full factorial repeated measures ANOVA (mixed-methods) was conducted based on sex and initial BMI (normal weight (NW), and overweight and obese (OW&OB)). Participants with the BMI of 18.5-24.9kg/m^2 were categorized as NW and those with a BMI $\geq 25$ kg/m^2 were grouped into the OW&OB category. This grouping was done due to the relatively lower number of subjects in the OW or OB categories compared to NW (control group was 69% NW (n=38) and 31% OW&OB (n=17) while the DSW+GF group was 75% NW (n=42) and 25% OW&OB (n=14)). A two-way repeated measures ANOVA was used to test the treatment effects on other anthropometrics (body fat, WC, HC, and waist-to-hip ratio (WHR)), systolic and diastolic blood pressure (SBP and DBP), and blood markers (Total Cholesterol (TC), Triglyceride (TG), High-density Lipoprotein (HDL), Low-density Lipoprotein (LDL), and TC/HDL) across all visits. Post hoc analyses were performed using a Tukey's test. Significance was set at  $p < 0.05$ , and data are presented as mean  $\pm$  SEM unless otherwise specified. Additionally, data collected from questionnaires (except the Likert item), was analyzed using a parallel multiple mediator model to test whether any component of participants' responses was a mediator for the impact of treatments.

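### Does a detectable effect of f = .15 overstate the trial's sensitivity to differences in change scores?

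*Combined protocol and SAP*

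**What the plan says.** The Statistical Analysis section reports "A sensitivity power analysis to determine the smallest detectable effect size" and says that it "was performed using G\*Power, 3.1.9.2". The assumption is that pre-holiday scores are "correlated with post-holiday with at least a correlation of" r = .40. The result is that "our study was poised to detect differences in change scores from time 1 to time 2 of" Cohen's f = .15, described in brackets as "small-to-medium) effects".

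The sentence does not give the power, the N entered, the G*Power module, the effect-size option or the SD that standardises f. Two inputs can be taken from the same section. The arm sizes come from the BMI breakdown: "control group was 69% NW (n=38) and 31% OW&OB (n=17) while the DSW+GF group was 75% NW (n=42) and 25% OW&OB (n=14". The significance level is .05. The analysis described next is a repeated measures ANOVA.

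**The concern.** Cohen's f has no fixed meaning until one knows which SD it is divided by. The sentence attaches f = .15 to differences in change scores, so a reader may take the divisor to be the SD of the change score. On that scale the trial cannot detect f = .15 with conventional power. The detectable value at 80% power is about 0.27, roughly 1.8 times larger and closer to what is usually called a medium effect.

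What would be at stake is how null results are read. This is the plan's only statement about sensitivity, and the plan tests many outcomes besides body weight: body fat, circumferences, blood pressure and lipids. A reader who credits the trial with good power for small-to-medium differences in change could take a non-significant result as stronger evidence of no effect than it is.

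**Working it through.** **Inputs**

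- Control: 38 + 17 = 55. DSW+GF: 42 + 14 = 56. N = 111 (Statistical Analysis). That this N was used in the sensitivity run is inferred.
- Alpha = .05 and r = .40 (Statistical Analysis).
- Two groups (Study Protocol) and two times (the sensitivity sentence names time 1 to time 2).
- Power: not stated; 80% assumed, with 75%, 90% and 95% also tried.
- Module: not stated; repeated measures ANOVA, within-between interaction, default f assumed.

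**Step 1. Reproduce the plan's figure.** For the interaction with m = 2 times, the noncentrality is

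λ = N f² m / (1 − r) = 111 × .0225 × 2 / .60 = 8.325,

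referred to F with 1 and 109 degrees of freedom. Power at f = .15 is 81.6%. Solving for 80% power gives f = .147, which rounds to .15.

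Other two-group, two-time options at 80% power do not give .15: the between-groups effect gives 0.225, a one-way ANOVA on change scores 0.268, and G*Power's SPSS-style effect size 0.271. The same interaction calculation at 90% and 95% power gives 0.170 and 0.189. A three-visit version with two groups at 90% power gives 0.152, but the sentence concerns two times only.

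**Step 2. Convert to change-score units.** The interaction f is in single-visit SDs.

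- Difference in change = 4f = 4 × .15 = 0.60 single-visit SD.
- SD of change = √(2(1 − r)) = √1.2 = 1.095 single-visit SD.
- d on change scores = 0.60 / 1.095 = 0.548, so f = 0.548 / 2 = 0.274.
- At exactly 80% power (f = .147): d = 0.537, f = 0.268.

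The noncentrality is unchanged: 0.274² is .075 before rounding, and 111 × .075 = 8.325. So .15 and 0.274 are one detectable difference in two units. The ratio √(2 / (1 − .40)) = 1.83 is a unit conversion, not lost power.

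**Step 3. Check with a direct two-group t test on change scores, 55 v 56.**

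| Power | d | f |
|---|---|---|
| 75% | 0.505 | 0.252 |
| 80% | 0.537 | 0.268 |
| 90% | 0.621 | 0.310 |
| 95% | 0.69 | 0.345 |

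If f = .15 (d = 0.30) were in change-score units, λ would be 111 × .0225 = 2.498 and power 34.7%. The stated figure therefore cannot be in those units at any of these powers.

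**Step 4. Vary r at 80% power.**

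| r | f, single-visit SD | f, change-score SD |
|---|---|---|
| .40 | .147 | 0.268 |
| .60 | .120 | 0.268 |
| .80 | .085 | 0.268 |
| .90 | .060 | 0.268 |
| .98 | .027 | 0.268 |

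The correlation affects only the single-visit f. On the change-score scale it drops out.

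**The case for a change.** The best case for a change is that a sensitivity claim should be true on the scale it names, and this one names change scores. The reader is not told the unit, and recovering it takes the calculation above. The direction does not rest on the inferred 80%: from 75% to 95% power the change-score f is never below 0.25. Correcting it would cost one sentence.

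Part of this stands. The sentence omits power, N, module and unit, and it can be misread. The rest is weaker:

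- The sentence opens with a correlation. Step 4 shows that a correlation is needed only for the single-visit f. A reader who assumes change-score units has to ignore the stated assumption, the named software and the repeated measures analysis that follows.
- The reference to change scores can fairly be taken as naming the contrast (group by time) rather than the standardiser.
- Giving r as a minimum is not a fault. The single-visit f falls as r rises, so the value at .40 is the least favourable one in the stated unit.
- The label small-to-medium goes with the f that is reported. Calling the effect medium means moving to another unit.
- The 35% power figure tests a claim that the plan does not clearly make.

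**Conclusion.** The concern does not hold as an error. The figure of .15 reproduces (.147 at 80% power, or 81.6% power at .15) as a group-by-time interaction effect in single-visit SDs. In change-score SDs the same difference is f of about 0.27, or d of about 0.54. Neither number is wrong, and the trial's sensitivity is the same in both.

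What remains is missing detail. The section is written in the past tense and already reports the group sizes, so the figure is not shown to have governed recruitment, and no test, estimate or decision rule uses it. Supplying the unit would change no result, and a statistician can recover the change-score equivalent from the numbers given.

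This rests on three inferences: 80% power, N = 111 and the default interaction module. If any is wrong, the account of how .15 arose is less certain. The change-score values for 55 and 56 participants would still stand at the powers tabulated. No figure in kg can be given, because the documents report neither the SD of change nor the observed correlation.

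### The analysis section labels no body-weight contrast as primary in a full factorial tested at p < 0.05; if any of four treatment terms were read as an effect, the false-positive chance would be about 17%

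*Combined protocol and SAP*

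**What the plan says.** The aim of the BW analysis is given as "To test the treatment effects on BW across visits, as well as on the change between visits". The method is that "a full factorial repeated measures ANOVA (mixed-methods) was conducted based on sex and initial BMI", with BMI in two groups. The only error criterion is p < 0.05, and the only adjustment is that "Post hoc analyses were performed using a Tukey's test".

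There are three visits. Of the third, the Follow-up Visit (v3) section says: "This visit occurred in HNL 14 weeks after v2 under the same conditions and procedures as v1 and v2". The sensitivity calculation concerns the first two only: "our study was poised to detect differences in change scores from time 1 to time 2", with Cohen's f = .15 and a pre/post correlation of at least .40. Its power and N are not stated.

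The cell sizes are given by arm and BMI group: "control group was 69% NW (n=38) and 31% OW&OB (n=17) while the DSW+GF group was 75% NW (n=42) and 25% OW&OB (n=14". The split by sex is not given. Randomisation used "balanced blocks by age, sex, and BMI".

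**The concern.** The study was sized on one comparison, the difference between arms in v1-to-v2 change, but the BW analysis is described as a whole factorial. A full factorial of treatment, visit, sex and BMI group contains eight terms that involve treatment. Four of them concern treatment on change: treatment x visit, and that term crossed with sex, with BMI group, and with both. None is labelled as the main test, and Tukey on post hoc pairs does not control error across the model's F tests. A report could therefore present whichever term reached p < 0.05 as the BW effect, and that result would be weaker evidence than it looks.

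There is also a question of precision. When treatment interacts with sex and BMI in the model, the treatment x visit contrast depends on how the sex-by-BMI cells are weighted. The weighting is not stated. Equal weighting of very unequal BMI groups is less precise than the two-group comparison behind f = .15.

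**Working it through.** **Inputs from Statistical Analysis.** Control 38 + 17 = 55; DSW+GF 42 + 14 = 56; N = 111; r = .40; f = .15; alpha = .05.

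**Assumptions.** Power for the stated f; the sex split (balanced across arms); one crossed model.

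**1. The plan's own figure.** For a two-group, two-visit interaction, lambda = f² x N x m / (1 - r) = .0225 x 111 x 2 / .60 = 8.325. With F(1, 109), power is .816, and the detectable f at 80% power is .147, which rounds to .15. This match is not unique: three visits at 90% power give f = .152.

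**2. False positives, conditional on reading any of four terms as an effect.**
- If the four tests were independent: 1 - .95⁴ = 18.5%.
- Simulated null v1-to-v2 changes (40,000 data sets per sex split, documented arm-by-BMI cells, eight-cell model with a shared residual), equal-weighted tests: 17.4% at a 50/50 sex split, 17.3% at 60/40, 16.3% at 70/30 and 15.7% at 80/20.
- Sequential tests on the same data: 18.1-18.7%.
- One named contrast: 5%.

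The result is therefore about 17%, with a range of 16-19%. It hardly depends on the unreported sex split. In three-visit simulations with r from .4 to .9 it was 16.5-17.6%, so it hardly depends on r either.

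**3. Precision, conditional on equal weighting** (variance of the contrast in units of the residual variance of change).
- Two-group: 1/55 + 1/56 = .03604.
- Equal weight over BMI groups: ¼ x (1/38 + 1/17 + 1/42 + 1/14) = .04509. Ratio .04509 / .03604 = 1.25.
- Equal weight over sex as well, in whole-number cells: ratio 1.25 at 50/50, 1.29 at 60/40, 1.51 at 70/30.
- Stratified by BMI without treatment x BMI: 1 / (38 x 42/80 + 17 x 14/31) = .03620. Ratio 1.004, power .814. Weighting by observed stratum sizes gives the same ratio.

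Power at f = .15, with an even sex split for the equal-weighted test:

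| r | two-group | equal-weighted |
|---|---|---|
| .4 | .816 | .724 |
| .6 | .939 | .879 |
| .7 | .981 | .951 |
| .8 | .999 | .993 |
| .9 | >.999 | >.999 |

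At 70/30 the equal-weighted figures are .642 at r = .4 and .980 at r = .8.

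**4. Offset from adjustment.** The comparison in step 3 holds residual variance equal. If sex and BMI explained 1 - 1/1.251 = 20% of the variance of change, the equal-weighted test would regain the planning power at r = .4 (.815). The documents give no figure for this share.

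**5. Interaction terms.** The treatment x BMI contrast has variance 4 x .04509 = .1804. For an interaction as large as f = .15, power is .25 at r = .4 and .88 at r = .9.

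**The case against.** Several points on the other side stand.

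- A reader might infer that the plan has a 17% false-positive rate. The documents do not support that. Treatment x sex and treatment x BMI are questions about effect modification, and nothing says that a significant interaction counts as a treatment effect.
- A reader might infer that the main question cannot be identified. It can be inferred: the Intervention Period section places the intervention between v1 and v2, the Post-Holiday Visit section lets daily weighing stop at v2, and the power sentence concerns the same interval. What is missing is a label and a rule.
- A reader might infer that the study has less power than claimed. That needs equal weighting, which is not stated, and r near .40, which is given as a floor. It also needs sex and BMI to explain little of the variance of change. No power is stated to serve as a benchmark, and neither weighting is wrong in itself.
- A reader might infer that no primary test is named anywhere. The pages before Study Protocol were not available, so the claim is limited to the sections from there on.
- The analysis could have been run separately by sex and by BMI group. One crossed model is the more natural reading, but the count of four terms depends on it.

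These points limit the concern but do not remove it. The section that should designate the main BW test does not do so, and it gives no rule for multiplicity across model terms.

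**Conclusion.** The point holds as a conditional one. The available sections label no BW contrast as primary, and the factorial is tested at p < 0.05 per term. The chance of at least one false positive among the four treatment terms on v1-to-v2 change is about 17% (16-19%), and it applies only if any of the four is read as a treatment effect. For treatment x visit alone it is 5%.

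The precision point is secondary. With equal weighting over BMI groups the variance is about 25% larger, and more if sex is unbalanced. At r = .40 this takes power at f = .15 from .82 to .72. At r of .8 or more with an even sex split the loss is negligible. These figures assume 80% power behind f = .15, N = 111 and equal residual variance.

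The analysis is not invalid. Adjusting for sex and BMI is right, since both are balancing factors. The change is worth making because it is cheap and ties the main result to the comparison on which the study was sized.

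**What to change.** 1. Present the v1-to-v2 treatment x visit contrast as the main BW test. Take it from a model with age, sex and BMI group, each by visit (the three balancing factors), and no treatment x sex or treatment x BMI terms. Alternatively, keep the full factorial and state that the contrast is weighted by observed stratum sizes. For BMI, either choice costs about 0.4% in variance. The cost of the age term was not calculated, because the age distribution is not given.
2. State that f = .15 refers to this contrast, and give the power and N assumed.
3. Label the v2-to-v3 and all-visit tests secondary. Report treatment x sex and treatment x BMI as exploratory estimates with 95% confidence intervals, and give the eight arm-by-sex-by-BMI cell sizes.
4. The section is written in the past tense, so disclose that the label is post hoc and show the original full-factorial result beside it. Do not claim that relabelling secures a 5% error rate: disclosure reduces that problem but does not remove it.

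The cost is a change of wording and one re-run of the BW model, with no new data. The downside is that subgroup results become exploratory.

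### The 11 outcomes other than body weight are analysed by repeated measures ANOVA with v1 in the response; adjusting for v1 as a covariate would give intervals about 2.5% to 16% narrower.

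*Combined protocol and SAP*

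**What the plan says.** The Statistical Analysis section describes two kinds of model.

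- **Body weight.** The aim is given as "To test the treatment effects on BW across visits, as well as on the change between visits". The model is a full factorial repeated measures ANOVA that includes sex and initial BMI class (normal weight against overweight and obese).
- **Other outcomes.** "A two-way repeated measures ANOVA was used to test the treatment effects on other anthropometrics", and likewise on blood pressure and blood markers, over all visits. The list is body fat, WC, HC, WHR, SBP, DBP, TC, TG, HDL, LDL and TC/HDL: 11 outcomes. No covariate is named.

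The sensitivity power analysis takes pre-holiday scores to be "correlated with post-holiday with at least a correlation of" .40, and concludes that "our study was poised to detect differences in change scores from time 1 to time 2" of Cohen's f = .15. No correlation is given for any single outcome.

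The v1 values exist. The Pre-Holiday Visit section lists "Height, body weight (BW), waist and hip circumference (WC and HC), blood pressure, and body composition" by DXA, and adds "A fasting blood draw was taken for blood lipids". The v2 visit repeated the v1 procedures. On v3 the plan says: "This visit occurred in HNL 14 weeks after v2 under the same conditions and procedures as v1 and v2".

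**The concern.** In a two-way group-by-visit ANOVA the v1 mean of each group is estimated freely, although randomisation makes the two groups equal at v1 in expectation. The treatment contrast for v2 is then a difference in change scores, which subtracts the whole of the v1 value. Unless r is close to 1 (with equal variances), that is more than the best prediction of v2 from v1 would subtract, and the excess is noise. Using v1 as a covariate subtracts only the predictive part.

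At stake is the width of the intervals for the 11 outcomes whose models have no other baseline term. With 111 participants, a wide interval can leave a moderate effect on blood pressure or lipids unresolved when data already in hand could narrow it.

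**Working it through.** **Inputs.** From the Statistical Analysis section: control 38 + 17 = 55, DSW+GF 42 + 14 = 56, total 111; r at least .40; f = .15; alpha .05. Assumed: complete data, 80% power where power is used (the plan states none), r = .7 and .9 as further examples, and equal v1 and v2 SDs unless varied below. Differences are in units of that SD.

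**1. The plan's own figure.** For a group-by-visit interaction with 2 groups and 2 visits, lambda = f² × N × 2/(1 − r) = .0225 × 111 × 2/.6 = 8.325. On F(1, 109) this gives power .816. The smallest f at 80% power is .147, which rounds to the plan's .15, so the figure reproduces. With 55 × 56/111 = 27.75, it equals a group difference in change of √(8.325 × 1.2/27.75) = 0.600 SD.

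**2. Variance of the two contrasts.** Change score: 2(1 − r)/27.75. Adjusted for v1: (1 − r²)/27.75. Ratio: (1 − r²)/[2(1 − r)] = (1 + r)/2.

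| r | Variance ratio | SE ratio | 95% half-width, change to adjusted (SD) | Detectable difference at 80% power (SD) |
|---|---|---|---|---|
| .40 | .70 | .837 | .412 to .345 | .588 to .492 |
| .7 | .85 | .922 | .291 to .269 | .416 to .383 |
| .9 | .95 | .975 | .168 to .164 | .240 to .234 |

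The SE ratios correspond to intervals about 16%, 8% and 2.5% narrower. Change scores use 109 degrees of freedom and the adjusted model 108.

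**3. Cost of estimating the slope.** In simulation with 111 participants (8,000 runs) the mean SE moved from .2074 to .1743 at r = .40, .1469 to .1361 at .7, and .0847 to .0830 at .9. Squaring the ratios gives .706, .858 and .959, so little of the gain is lost. For a 0.40 SD effect (an assumption), power is 47.9% on change at r = .40. With v1 adjustment it is 62.5% ignoring slope estimation. Inflating the variance by 1 + 1/107 for the slope makes it 62.1%. At r = .7 the three figures are 76.9%, 83.3% and 82.9%. The slope therefore costs about 0.4 points.

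**4. Unequal variances.** If the v2 SD is s times the v1 SD, the ratio is s²(1 − r²)/(1 + s² − 2rs). For s = 0.9 and r = .40: .81 × .84/1.09 = .62. For s = 1.1 and r = .40: 1.21 × .84/1.33 = .76.

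| s | r = .40 | r = .7 | r = .9 |
|---|---|---|---|
| 0.9 | .62 | .75 | .81 |
| 1.0 | .70 | .85 | .95 |
| 1.1 | .76 | .92 | 1.00 |

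The gain therefore depends on both r and s, and can vanish when r is high and the spread grows.

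**The case against.** The strongest reply is that nothing here is wrong. A group-by-visit test is a valid analysis of a randomised three-visit trial, and the plan is coherent: its sensitivity analysis concerns change scores, and so does its contrast. That stands. A reader might infer bias from the missing covariate, but participants were randomised and the documents give no ground for it.

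A reader might also apply the ratios to every outcome. For body weight that goes too far. Its model already carries initial BMI class, a coarse baseline adjustment, and its r is probably high (an assumption), so the further gain is probably small.

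Nor is r simply unstated: the plan gives a floor of .40. What is missing is a value for each outcome. Because .40 is a floor, .70 is the largest gain under equal variances, not a typical one.

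The power figures need care. At r = .40, a 0.60 SD effect goes from 81.6% to 92.8% power, but at .7 it goes only from 98.1% to 99.2%. Since the analyses are reported as already performed, an added analysis cannot claim power for new tests. What it delivers is narrower intervals.

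Finally, one could suppose that the treatment test is a group effect averaged over visits including v1, which would dilute the effect far more. The plan does not say which ANOVA term is tested, and its power statement points to change scores, so the point is not rested on that reading.

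**Conclusion.** The point holds for the 11 outcomes analysed by two-way ANOVA, as an avoidable loss of precision. With equal v1 and v2 variances and complete data, v1 adjustment would narrow 95% intervals by about 16% at the plan's floor of r = .40, 8% at .7 and 2.5% at .9. If the SD changes by 10% between visits, the variance ratios range from .62 to 1.00 over the same values of r. The documents do not allow a closer statement, because they give no r and no SD for any outcome. The existing analysis remains valid and none of its conclusions is overturned.

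**What to change.** For each of the 11 outcomes, and optionally body weight, fit a model with v2 and v3 as responses and the v1 value as covariate, with its slope allowed to differ by visit. Report the adjusted group difference with its 95% interval at v2 as the main contrast, since that is the end of the intervention (there "The DSW+GF group was told they could discontinue DSW"), and at v3, 14 weeks later, as secondary. Place these beside the existing ANOVA and label them supplementary, because the section describes analyses already done. State the observed v1–v2 correlation and both SDs for each outcome, so that the actual gain can be seen.

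Do not add age, sex and BMI on precision grounds. In simulation with pairs blocked on these factors (an assumed form of the blocking), they gave no gain worth claiming at r of .7 or above.

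The cost is one re-analysis and one table, with no new data. The covariate takes one degree of freedom plus slope estimation, up to about 0.4 points of power for a 0.40 SD effect. It adds 11 × 2 = 22 post hoc estimates (24 with body weight). Read as tests at .05, 24 would give 24 × .05 = 1.2 expected false positives under the null, and a 1 − .95²⁴ = 71% chance of at least one if independent (less if the outcomes are correlated). They should be presented as estimates, not as new significance claims.
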